16.3.3. SUBGROUP ANALYSIS OF LABORATORY VALUES

The following laboratory parameters will be evaluated for the subgroups specified in section 7.5: serum prolactin, blood glucose, HbA1c(NGSP), glycoalbumin (absolute and percentage), total cholesterol, LDL cholesterol, HDL cholesterol, HOMA-IR and triglycerides. These parameters will be separated by fasting status for the subgroup analyses, with the exception of prolactin, HbA1c and glycoalbumin.

For these subgroup analyses, these selected parameters will be summarized by Observed and change from baseline at Week 6 (LOCF), including a nonparametric rank ANCOVA test. The same analysis methods will be performed as detailed in section 15.2.4.

16.4. ECG EVALUATIONS

Results from the central [REDACTED] will be included in the reporting of this study.

A LOCF endpoint will also be derived for ECG. For calculation details, please see section 6.3.

The following ECG parameters will be reported for this study:

Document:	K:\DSP\SM-13496\KVA95374\Biostatistics\Documentation\SAP	Version Number:	1.0
Author:	[REDACTED]	Version Date:	30MAR2017

Template No: CS_TP_BS016 – Revision 3
 Effective Date: 01May2012

Reference: CS_WI_BS005

Copyright © 2012 [REDACTED] All rights reserved. [REDACTED] Unauthorized use, disclosure or reproduction is strictly prohibited.

- Heart Rate (bpm)
- PR Interval (msec)
- QRS Interval (msec)
- RR Interval (msec)
- QT Interval (msec)
- QTcF Interval (msec)
- QTcB Interval (msec)
- Overall assessment of ECG:
 - o Normal
 - o Abnormal

The following summaries will be provided for ECG data:

- Observed baseline and change from baseline by visit (for quantitative measurements)
- Shift from baseline according to abnormal criteria (for overall assessment)
- Incidence of QTc Prolongation (see section 16.4.3)
- Summary of patients with abnormal ECG values (see section 16.4.2)
- Listing of patients with prolonged QTc results

16.4.1. ECG SPECIFIC DERIVATIONS

All required ECG parameters are available in the data provided for analysis. There are no ECG parameters to be derived.

16.4.2. ECG ABNORMAL CRITERIA

The individual ECG measurements would be noted as abnormal if exceeding the values indicated in Table D:

Table D: Abnormal ECG Values by parameter

ECG Parameter	Abnormal
HR (bpm)	≥ 100 bpm
PR interval (msec)	≥ 210 msec
QRS interval (msec)	≥ 120 msec

Document: K:\DSP\SM-13496\KVA95374\Biostatistics\Documentation\SAP

Author:

Version Number:

1.0

Version Date:

30MAR2017

Template No: CS_TP_BS016 – Revision 3

Reference: CS_WI_BS005

Effective Date: 01May2012

Copyright © 2012 All rights reserved.

The contents of this document are confidential and proprietary to . Unauthorized use, disclosure or reproduction is strictly prohibited.

QT interval (msec)	> 500 msec
--------------------	------------

16.4.3. ECG MARKEDLY ABNORMAL CRITERIA

Markedly abnormal quantitative ECG measurements will be identified in accordance with the following predefined markedly abnormal criteria:

- Absolute values for QTcB interval and QTcF will be classified as:
 - o > 450 msec
 - o > 480 msec
 - o > 500 msec
- Change from Baseline for QTcB interval and QTcF will be classified as:
 - o ≥ 30 msec increase from baseline
 - o > -60 msec increase from baseline

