3.5 Sample size

The target number of the randomized patients is 501 (ie, 167 patients per treatment group)

Rationale

The sample size for the study has been determined by a Monte-Carlo simulation using the Statistical Analysis Software (SAS Version 9.2, SAS Institute). The sample size calculation is based on the number of patients required for the primary analysis in the intention-to-treat (ITT) population, where the primary analysis is performed on the change from baseline in the MADRS total score at Week 6. Hochberg procedure will

be utilized for the multiplicity adjustment to the multiple comparisons between each SM-13496 (20-60 and 80-120 mg/day) group and the placebo group.

A common effect size of 0.35 (ie, an intergroup difference in change from baseline of 3.5 with a standard deviation of 10) in the MADRS total score for both SM-13496 groups over placebo group was used for estimating the sample size. A sample size of 161 per group for a total of 483 patients was estimated to yield a complete power (probability of rejecting 2 null hypotheses) of 80%, with a one-sided 2.5% significance level using Hochberg procedure for multiplicity adjustment. Considering the possibility of patients who are randomized but who do not provide any post-baseline MADRS total score, the total sample size will therefore be 501 patients or 167 patients per treatment group.

The assumed effect size of 0.35 has been determined based on the PREVAIL 2 study of which study design is similar to that of the present study. In the PREVAIL 2 study, the sample size had been calculated with effect sizes of 0.39 for both SM-13496 groups (20-60 and 80-120 mg/day), and as a result, effect sizes were 0.45 for both SM-13496 groups over the placebo group on the change from baseline at Week 6 (last observation carried forward [LOCF]) in the MADRS total score. The result of the PREVAIL 2 study is shown in Table 2.

Table 2 Change from baseline in the MADRS total score at Week 6 (LOCF) – Analysis of Covariance –, Intention-to-Treat population, in the PREVAIL 2 study

	SM-13496 20-60 mg/day (N=161)	SM-13496 80-120 mg/day (N=162)	Placebo (N=162)
LS mean (SE)	-13.9 (0.80)	-13.9 (0.78)	-9.5 (0.79)
Inter-treatment difference vs. placebo (SE)	-4.5 (1.10)	-4.4 (1.10)	
Effect size	0.45	0.45	

LS means are from an analysis of covariance (ANCOVA) with treatment and pooled study site as fixed factors and baseline value as a covariate.

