9.7.6 Laboratory tests, vital signs, body weight, and 12-lead ECG

Summary statistics for laboratory tests, vital signs, body weights, and 12-lead ECG parameters will be provided by treatment group. Continuous variables will be summarized using descriptive statistics of number of patients, mean, median, standard deviation, minimum, and maximum values. Categorical variables will be reported as frequencies and percentages. Laboratory tests as a categorical variable will be reported for shift tables. A rank ANCOVA method with adjustments for baseline value will be applied to change from baseline to Week 6 (LOCF) in serum prolactin, fasting blood glucose, HbA1c (NGSP), glycoalbumin, total cholesterol, LDL cholesterol, HDL cholesterol, triglycerides, and body weight for comparison between each SM-13496 (20-60 and 80-120 mg/day) group and the placebo group.

Laboratory data will be summarized by the flagging of abnormal values in data listings. The incidence of markedly abnormal post-baseline laboratory values (MAPLV), markedly abnormal post-baseline vital signs (MAPVS), and prolonged QTc will be summarized by treatment group. In these analyses, post-baseline laboratory test values obtained at unscheduled visits will be taken into consideration.

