6.7. COMMON CALCULATIONS

For quantitative measurements, change from baseline will be calculated as:

- Test Value at Visit X – Baseline Value

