16.5.2. VITAL SIGNS MARKEDLY ABNORMAL CRITERIA

Markedly abnormal quantitative Vital Signs measurements will be identified in accordance with the following predefined markedly abnormal criteria.

Variable	Unit	Low	High
SBP	mmHg	≤ 90 mmHg AND change from baseline ≤ -20 mmHg	≥ 180 mmHg AND change from baseline ≥ 20 mmHg
DBP	mmHg	≤ 50 mmHg AND change from ≤ -15 mmHg	≥ 105 mmHg AND change from baseline ≥ 15 mmHg
Pulse rate	Bpm	≤ 50 bpm AND change from baseline ≤ -15 bpm	≥ 120 bpm AND change from baseline ≥ 15 bpm
Body temperature	°C	NA	≥ 38.3 °C AND change from baseline ≥ 0.8 °C
Weight	Kg	percentage change from baseline ≤ -7.0 %	percentage change from baseline ≥ 7.0 %

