17. DATA NOT SUMMARIZED OR PRESENTED

The other variables and/or domains not summarized or presented are:

- Comments
- MINI screening questionnaire

These domains and/or variables will not be summarized or presented, but will be available in the clinical study database, SDTM and/or ADaM datasets.

Document: K:\DSP\SM-13496\KVA95374\Biostatistics\Documentation\SAP

Author: [REDACTED]

Version Number:

1.0

Version Date:

30MAR2017

Template No: CS_TP_BS016 – Revision 3

Reference: CS_WJ_BS005

Effective Date: 01May2012

Copyright © 2012 [REDACTED] All rights reserved.

The contents of this document are confidential and proprietary to [REDACTED]. Unauthorized use, disclosure or reproduction is strictly prohibited.

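### As extracted, the second QTc change class in SAP 16.4.3 carries a minus sign; coded literally, it would take in nearly every patient and could not show large prolongations

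*SAP*

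**What the plan says.** Protocol 9.7.6 asks that the incidence of "prolonged QTc will be summarized by treatment group" but gives no cut-off. The cut-offs are in the SAP. SAP 16.4 lists among its ECG outputs "Incidence of QTc Prolongation (see section 16.4.3", which sends the reader to SAP 16.4.3.

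SAP 16.4.3 defines five classes for QTcB and QTcF. Three are absolute: above 450, 480 and 500 msec. Two are changes from baseline. The first is "≥ 30 msec increase from baseline". The second, as extracted, is "> -60 msec increase from baseline".

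The sign convention is set in SAP 6.7, where change is "Test Value at Visit X – Baseline Value". A fall in QTc is therefore a negative number.

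Neither document states a QTc change cut-off anywhere else. Table D in SAP 16.4.2 covers heart rate, PR, QRS and uncorrected QT, but not QTc.

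**The concern.** A change greater than -60 msec is met by any rise, by no change, and by any fall smaller than 60 msec. The class listed second, where the more extreme one would be expected, is then far wider than the 30 msec class it should sit inside.

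QTc is named in the sixth secondary objective. Protocol 9.7.6 does not include QTc among the variables for rank ANCOVA, and SAP 16.4 plans no overall between-arm test of it. The overall QTc assessment therefore rests on descriptive and categorical outputs. A row that is nearly full in all three arms would carry no information about large prolongations. If the listing of prolonged QTc results used the same rule, it would fill with patients who had no prolongation.

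**Working it through.** The plan states no figure to reproduce, so the check is of the rule's logic, followed by an illustration of size.

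**Step 1: the line against its context.**
- *Wording.* The line calls a negative threshold an increase. Where the SAP means a fall it writes it differently: the low systolic pressure criterion in SAP 16.5.2 is "≤ 90 mmHg AND change from baseline ≤ -20 mmHg". That has a less-than-or-equal sign, a negative number and no mention of an increase.
- *Purpose.* SAP 16.4 and Protocol 9.7.6 both use these criteria to count prolongation. A class that admits falls cannot measure that.
- *Ordering.* The absolute classes run from mild to extreme (450, 480, 500 msec). The change classes should do the same. Every change of 30 msec or more also exceeds -60 msec, so as written the second class contains the first.

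**Step 2: size under a literal reading.** The documents give no mean or SD for QTc change, so both are assumed: mean m from -5 to +5 msec, SD s from 10 to 30 msec, normal distribution. Protocol 6.4.4 schedules one ECG after baseline (Visit 8 or discontinuation), so one change per patient is a fair simplification.

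- Flagged as written: P(change > -60) = 1 - Φ((-60 - m)/s)
- Falls among those flagged, as a share of all patients: P(-60 < change < 0) = Φ(-m/s) - Φ((-60 - m)/s)
- 30 msec class: P(change ≥ 30) = 1 - Φ((30 - m)/s)
- Positive 60 msec class: P(change ≥ 60) = 1 - Φ((60 - m)/s)

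| m | s | > -60 | fall of less than 60 | ≥ 30 | ≥ 60 |
|---|---|---|---|---|---|
| -5 | 10 | 100.0% | 69.2% | 0.02% | 0.0% |
| -5 | 30 | 96.7% | 53.3% | 12.2% | 1.5% |
| 0 | 20 | 99.9% | 49.9% | 6.7% | 0.1% |
| 0 | 30 | 97.7% | 47.7% | 15.9% | 2.3% |
| 5 | 10 | 100.0% | 30.9% | 0.6% | 0.0% |
| 5 | 30 | 98.5% | 41.9% | 20.2% | 3.3% |

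The lowest value in the third column comes from m = -5, s = 30: (-60 + 5)/30 = -1.833, and 1 - Φ(-1.833) = 0.9666. The highest value in the last column comes from m = 5, s = 30: (60 - 5)/30 = 1.833, and 1 - Φ(1.833) = 0.0334.

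**Step 3: as counts.** Protocol 3.5 says: "The target number of the randomized patients is 501". Taking that as the denominator, for scale only, the literal rule flags at least 501 × 0.9666 = 484 patients and at most all 501. A positive 60 msec class would flag between 0 and 501 × 0.0334 = 17.

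**The case against.** Three objections deserve weight.

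First, the minus sign may not be in the plan. The text extracted from the PDF contains character misreads. For example, the footer code in SAP section 17 appears as "Reference: CS_WJ_BS005", while elsewhere its middle part ends in I rather than J. A greater-than-or-equal sign whose lower bar became detached could look like what we see. Against that, the 30 msec line directly above was read cleanly, so a genuine typing error cannot be excluded. The text alone does not settle it.

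Second, a reader might infer that nearly every patient will be counted as markedly abnormal. The documents do not support that as a forecast. The line itself refers to a rise, and the section exists to count prolongation. The outcome follows only if a programmer codes the sign literally and nobody questions a prolongation row near 100% on placebo. This objection stands, so the consequence is stated here only as conditional.

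Third, a reader might infer that the QTc evaluation as a whole is compromised. It is not. One class of five is affected. Anyone with a rise of 60 msec or more is already in the 30 msec class, and the 450, 480 and 500 msec classes work as written. SAP 16.4 also plans baseline and change summaries by visit, and SAP 7.5, 15.2.4 and 16.4.4 plan subgroup analyses of QTc. The row meant to isolate the largest rises would still be lost.

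**Conclusion.** Minor; wrong as written, subject to checking the original page. As extracted, the second change class contradicts its own wording, its purpose and its position, and no other section corrects it. Followed literally, it would put about 97% to 100% of patients in the class in every arm, against 0% to about 3% for a positive 60 msec class. These percentages rest on a normal distribution with the assumed means and SDs above. The logical contradiction needs no such assumption.

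A positive 60 msec increase is the evident intent, but the documents do not state it. A reader might also infer that the operator must match the 30 msec line. The documents leave that open: the extracted line uses a strict inequality, as do the absolute classes, while the 30 msec class includes its boundary. No efficacy result, significance level or sample size is touched.

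**What to change.** 1. Check SAP 16.4.3 on the original page. If the minus sign is absent there, nothing in the plan needs changing.
2. If it is present, remove it so that the class is a positive 60 msec increase for QTcB and QTcF, nested inside the 30 msec class.
3. Have the sponsor confirm whether 60 msec itself is included (> or ≥), and write that operator in.
4. Apply the same cut-off in the QTc prolongation incidence table and the listing of prolonged QTc results.

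The cost is one corrected line before programming, with no new data.

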16.4.4. SUBGROUP ANALYSIS OF ECG VALUES

Observed baseline and change from baseline by visit analyses will be repeated by subgroups as defined in section 7.5 for QTcB interval and QTcF interval only. For the methodology please see section 15.2.4.

16.5. VITAL SIGNS

The following Vital Signs measurements will be reported for this study:

- Systolic Blood Pressure (mmHg)
- Diastolic Blood Pressure (mmHg)
- Pulse Rate (bpm)
- Temperature ($^{\circ}\text{C}$)
- Weight (kg)
- BMI (kg/m^2)

The following summaries will be provided for vital signs data:

- Observed baseline and change from baseline by visit
- Incidence of markedly abnormal values
- Listing of patients meeting markedly abnormal post-baseline vital signs (MAPVS) criteria

Document: K:\DSP\SM-13496\KVA95374\Biostatistics\Documentation\SAP

Author: [REDACTED]

Version Number:

1.0

Version Date:

30MAR2017

Template No: CS_TP_BS016 – Revision 3

Reference: CS_WI_BS005

Effective Date: 01May2012

Copyright © 2012 [REDACTED] All rights reserved.

The contents of this document are confidential and proprietary to [REDACTED]. Unauthorized use, disclosure or reproduction is strictly prohibited.

Additionally, a rank ANCOVA (vs placebo) analysis will be performed for weight and BMI.

16.5.1. VITAL SIGNS SPECIFIC DERIVATIONS

No additional vital signs parameters are required.

16.5.2. VITAL SIGNS MARKEDLY ABNORMAL CRITERIA

Markedly abnormal quantitative Vital Signs measurements will be identified in accordance with the following predefined markedly abnormal criteria.

Variable	Unit	Low	High
SBP	mmHg	≤ 90 mmHg AND change from baseline ≤ -20 mmHg	≥ 180 mmHg AND change from baseline ≥ 20 mmHg
DBP	mmHg	≤ 50 mmHg AND change from ≤ -15 mmHg	≥ 105 mmHg AND change from baseline ≥ 15 mmHg
Pulse rate	Bpm	≤ 50 bpm AND change from baseline ≤ -15 bpm	≥ 120 bpm AND change from baseline ≥ 15 bpm
Body temperature	°C	NA	≥ 38.3 °C AND change from baseline ≥ 0.8 °C
Weight	Kg	percentage change from baseline ≤ -7.0 %	percentage change from baseline ≥ 7.0 %

16.5.3. SUBGROUP ANALYSIS OF VITAL SIGNS VALUES

Observed baseline and change from baseline by visit analyses will be repeated by subgroups as defined in section 7.5 for weight and BMI only. For the methodology please see section 15.2.4.

16.6. PHYSICAL EXAMINATION

Physical Examination results will be listed.

Document: K:\DSP\SM-13496\KVA95374\Biostatistics\Documentation\SAP
 Author: [REDACTED] Version Number: 1.0
 Version Date: 30MAR2017

Template No: CS_TP_BS016 – Revision 3 Reference: CS_WI_BS005
 Effective Date: 01May2012

Copyright © 2012 [REDACTED] All rights reserved.
 The contents of this document are confidential and proprietary to [REDACTED]. Unauthorized use, disclosure or reproduction is strictly prohibited.

16.7. OTHER SAFETY ASSESSMENTS

16.7.1. DRUG-INDUCED EXTRAPYRAMIDAL SYMPTOM SCALE (DIEPSS)

The DIEPSS is a clinician-rated assessment of extrapyramidal symptoms induced by antipsychotics and consists of eight individual parameters; gait, bradykinesia, sialorrhea, muscle rigidity, tremor, akathisia, dystonia, and dyskinesia; and one global assessment; overall severity. The severity of each item is graded 0 (normal) to 4 (severe), and then a summation of all questions (excluding overall severity) provides the total score which is used for analysis. The investigator will assess the DIEPSS at Visits 2 to 8 and at discontinuation. The assessment at Visit 8 or at discontinuation should be performed within 72 hours after the final administration of the study drug and before the initiation of post treatment with antipsychotics or the study drug in the long-term study.

A LOCF endpoint will also be derived for DIEPSS. For calculation details, please see section 6.3.

16.7.2. MISSING DATA METHODS

Missing question data for questionnaires is accounted for in the variable descriptions. The methods used for analysis of this endpoint will address visit data that is missing. In the event that any component element of the Total Score (Excluding Overall Severity) is missing, then this total score will be set to missing.

16.7.3. ANALYSIS OF QUALITY OF LIFE VARIABLES

16.7.3.1. Analysis of DIEPSS

The change from baseline in the DIEPSS total score (excluding overall severity) and the individual DIEPSS scores will be analyzed using the MMRM method described above for the primary efficacy variable. The change from baseline in the DIEPSS total score will also be analyzed using the LOCF ANCOVA method described for the primary efficacy variable, as a sensitivity analysis.

16.7.3.2. Subgroup Analysis of DIEPSS

Observed baseline and change from baseline by visit analyses will be repeated by subgroups as defined in section 7.5 for DIEPSS scores (excluding overall severity). For the methodology please see section 15.2.4.

16.7.4. COLUMBIA-SUICIDE SEVERITY RATING SCALE (C-SSRS)

The C-SSRS is a tool designed to systematically assess and track suicidal adverse events (suicidal behavior and suicidal ideation) throughout the study. The C-SSRS can comprehensively identify suicidal events and limit the over-identification of suicidal behavior. The rater will assess the C-SSRS at Visits 1 to 8 and at discontinuation. The 'baseline/screening' version will be used at Visit 1 and the 'since last visit' version at Visits 2 to 8 and at discontinuation. The assessment at Visit 8 or at discontinuation should be performed within 72 hours after the final administration of the study drug and before the initiation of post treatment with antipsychotics or the study drug in the long-term study.

Suicidal ideation is rated on a 6-point scale from 0='No ideation present' to 5='Active ideation with plan and intent'. A score of 4 or 5 on this scale indicates serious suicidal ideation. Intensity of ideation is measured in

Document:	K:\DSP\SM-13496\KVA95374\Biostatistics\Documentation\SAP		
Author:	[REDACTED]	Version Number:	1.0
		Version Date:	30MAR2017

Template No: CS_TP_BS016 – Revision 3
Effective Date: 01May2012

Reference: CS_WI_BS005

Copyright © 2012 [REDACTED] All rights reserved.

The contents of this document are confidential and proprietary to [REDACTED]. Unauthorized use, disclosure or reproduction is strictly prohibited.

terms of frequency, duration, controllability, deterrents, and reasons for ideation. Each is measured with responses ranging from 0 or 1 to 5, representing approximately less to more. The ideation intensity total score is the sum of the five preceding items and can range from 3 to 25 for patients with suicidal ideation endorsed.

Suicidal behavior is collected as presence/absence of actual attempts, non-suicidal self-injurious behavior, interrupted attempts, aborted attempts, preparatory acts or behavior, and any suicidal behavior. In addition, the number of actual attempts, interrupted attempts, and aborted attempts is captured. Any attempt will be defined as suicidal behavior. The lethality associated with actual attempts is rated on a 6-point scale from 0='No physical damage or very minor physical damage' to 5='Death'. Potential lethality of attempts is rated on a 3-point scale from 0='Behavior not likely to result in injury' to 2='Behavior likely to result in death despite available medical care'.

A composite measure of suicidality measures the presence of any suicidal ideation or behavior. The number and percentage of subjects with suicidality as measured by the C-SSRS will be summarized and compared among the SM-13496 treatment groups versus placebo using Fisher's exact test, where suicidality is defined as having at least one occurrence of suicidal ideation or at least one occurrence of suicidal behavior. The baseline suicidality indicator will be set to 1 if the subject exhibits suicidality during the two weeks prior to the baseline visit, 0 if the subject does not exhibit suicidality during the two weeks prior to the baseline visit, and missing otherwise. The post-baseline suicidality indicator is similarly defined for each post-baseline weekly visit. This analysis will be performed at Week 6, LOCF endpoint, and overall (based on all post-baseline visits up to and including LOCF endpoint) by treatment group and combined SM-13496 group.

An overall summary of post-baseline data across all visits up to and including LOCF endpoint will include the frequency and percentage of the following by treatment group and for the combined SM-13496 group:

- At least one suicidal ideation post-baseline
- No suicidal ideation post-baseline
- Emergence of suicidal ideation (no suicidal ideation at baseline, and any type of suicidal ideation post-baseline)
- Emergence of serious suicidal ideation (no suicidal ideation at baseline, and any serious suicidal ideation [ideation score of 4 or 5] post-baseline)
- Most severe type of ideation post-baseline
- Worsening of suicidal ideation (most severe suicidal ideation post-baseline was more severe than it was at baseline)
- At least one suicidal behavior post-baseline
- No suicidal behavior post-baseline
- Emergence of suicidal behavior (no suicidal behavior at baseline, and any type of suicidal behavior post-baseline)
- At least one actual attempt post-baseline
- At least one interrupted attempt post-baseline
- At least one aborted attempt post-baseline
- At least one preparatory act or behaviors post-baseline
- At least one instance of suicidality [any ideation or behavior] post-baseline
- No suicidality post-baseline

Document: K:\DSP\SM-13496\KVA95374\Biostatistics\Documentation\SAP

Author: [REDACTED]

Version Number:

1.0

Version Date:

30MAR2017

Template No: CS_TP_BS016 -- Revision 3

Reference: CS_WI_BS005

Effective Date: 01May2012

Copyright © 2012 [REDACTED] All rights reserved.

The contents of this document are confidential and proprietary to [REDACTED] reproduction is strictly prohibited.

Unauthorized use, disclosure or

- Emergence of suicidality (no suicidality at baseline, and any suicidality post-baseline)
- Any completed suicides post-baseline

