4.1.2 Exclusion criteria

Patients who meet any of the following criteria will be excluded from the study. If the patient eligibility is uncertain, the investigator should discuss enrollment of the patient with a medical monitor prior to randomization.

- 1) Patients who were diagnosed as having an Axis I or Axis II disorder (DSM-IV-TR criteria) other than bipolar I disorder that is the primary focus of treatment within 3 months prior to screening.
- 2) Patients with a score of ≥ 4 on the MADRS item 10 (suicidal thoughts) at screening or baseline.
- 3) Patients with a "Yes" response to the C-SSRS item 4 (active suicidal ideation with some intent to act, without specific plan) or item 5 (active suicidal ideation with specific plan and intent) at screening (within 6 months prior to screening) or baseline.
- 4) Patients with imminent risk of suicide or injury to self, others, or property.
- 5) Patients for whom diagnostic agreement (based on the Bipolarity Index) between the investigator and Bracket (Pennsylvania, the United States), the agency for computerized diagnosis, cannot be reached.
- 6) Patients with a history of non-response to 6-week trial of 3 or more antidepressants (with or without concomitant use of mood stabilizers) during the current episode.
- 7) Patients who had been hospitalized because of a manic or mixed episode within 60 days prior to screening.
- 8) Patients who received monoamine oxidase (MAO) inhibitor within 21 days prior to screening.
- 9) Patients who received fluoxetine or a combination of olanzapine and fluoxetine within 28 days prior to screening.

- 10) Patients who received any depot antipsychotics (sustained-release formulation) within 90 days prior to screening.
- 11) Patients who received clozapine within 120 days prior to screening.
- 12) Patients who received electroconvulsive therapy within 90 days prior to screening.
- 13) Patients with a $\geq 25\%$ reduction in the MADRS total score between screening and baseline.
- 14) Patients with a history of HIV seropositivity.
- 15) Patients with a history of alcohol/drug abuse (DSM-IV-TR criteria) within 3 months prior to screening or of alcohol/drug dependence (DSM-IV-TR criteria) within 12 months prior to screening. Exceptions include caffeine or nicotine abuse/dependence.
- 16) Patients with a history of hypersensitivity (eg, drug-induced anaphylaxis, rash, urticaria, or other allergic reactions) to more than one distinct chemical class of drug.

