16.1.7. ADDITIONAL AE SUMMARIES

- Summary of AEs by combined terms
- Summary of AEs occurring in $\geq 3\%$ of subjects. This summary will be repeated separated by country.
- Summary of AEs by exposure at earliest onset.
- Summary of AEs by preferred term by descending frequency

Document: K:\DSP\SM-13496\KVA95374\Biostatistics\Documentation\SAP

Author: [REDACTED]

Version Number:

1.0

Version Date:

30MAR2017

Template No: CS_TP_BS016 – Revision 3

Reference: CS_WI_BS005

Effective Date: 01May2012

Copyright © 2012 [REDACTED] All rights reserved.

The contents of this document are confidential and proprietary to [REDACTED]. Unauthorized use, disclosure or reproduction is strictly prohibited.

There will be no statistical comparisons between the treatment groups for safety data, unless otherwise specified with the relevant section.

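### The only formal between-arm suicidality comparison is a Fisher test that ignores baseline status and comes with no effect estimate or interval; a risk difference with 95% CI on emergence and worsening is needed.

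*SAP*

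**What the plan says.** The general safety statement in SAP Section 16 sets the default: "There will be no statistical comparisons between the treatment groups for safety data, unless otherwise specified with the relevant section". For suicidality, SAP 16.7.4 does specify one. The composite of any ideation or behaviour is "summarized and compared among the SM-13496 treatment groups versus placebo using Fisher's exact test, where suicidality is defined as having at least one occurrence" of either. The test is run at Week 6, at LOCF endpoint and over all post-baseline visits, by treatment group and for the combined SM-13496 group. A baseline suicidality indicator is defined, but the test does not use it. No risk difference, ratio or interval is mentioned.

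The same section lists rows that isolate new or worse events, such as "Emergence of suicidality (no suicidality at baseline, and any suicidality post-baseline"), and worsening of ideation. For these, the summary "will include the frequency and percentage of the following by treatment group and for the combined SM-13496 group"; no test or interval is given.

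On entry, Protocol 4.1.2 exclusion 3 removes patients positive on C-SSRS "item 4 (active suicidal ideation with some intent to act, without specific plan) or item 5". Exclusion 2 removes a MADRS item 10 score of 4 or more, and exclusion 4 removes imminent risk. Ideation at C-SSRS levels 1 to 3 is not in itself excluded.

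Protocol 9.7.3 plans only a descriptive summary. For treatment-emergent mania, SAP 16.7.5 plans a logistic model adjusted for baseline YMRS, with odds ratios and 95% CIs.

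**The concern.** Three features combine.

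- **Dilution.** A patient who ideates at entry and reports it again after baseline counts as an event, although nothing new has happened. Such events raise the rate in every arm and shrink the relative contrast.
- **Offsetting.** If treatment relieves ideation in patients who already had it, that benefit can cancel new events in patients who did not.
- **No interval.** A p-value does not show how large an increase remains compatible with the data.

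The protocol rationale (3.4.3) calls the suicide rate in bipolar disorder high and its prevention important. The trial has no data monitoring committee and no interim analysis, so the final tables carry the question. If the Fisher p-value exceeds 0.05, the plan offers no other inferential result to show how much or how little that means.

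**Working it through.** **Inputs from the documents.** 167 patients per arm, 1:1:1 (Protocol 3.5 and 4.2); two-sided 5% tests by default (SAP 6.6). No suicidality rate, baseline prevalence or persistence is given.

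**The plan's own sizing figure.** This concerns MADRS only: effect size 0.35, one-sided 2.5%, Hochberg, 161 per group, 80% power to reject both hypotheses. Simulating two comparisons that share one placebo arm gives about 80% at 161 and 82% at 167. The stated figure reproduces. Nothing was sized for suicidality.

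**Assumptions for suicidality.** Let b be the share ideating at baseline, s the share of those positive again after baseline, and q the emergent risk in the rest. The tested composite rate is

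b × s + (1 − b) × q.

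With b = 20%, s = 70%:

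- q = 5%: 0.14 + 0.04 = 18%
- q = 10%: 0.14 + 0.08 = 22%
- q = 15%: 0.14 + 0.12 = 26%

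A doubling of emergent risk becomes 18% versus 22%, and a tripling 18% versus 26%.

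**Power of the overall pairwise test.** This is exact Fisher power, summed over binomial outcomes, with rejection in the harmful direction and s = 70%. The last two columns apply the same test to emergence among baseline-negative patients only, with (1 − b) × 167 per arm.

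| b | Composite, 5% v 10% | Power | Composite, 5% v 15% | Power | n per arm, emergence | Power, 5% v 10% / 5% v 15% |
|---|---|---|---|---|---|---|
| 0% | 5 v 10 | 33% | 5 v 15 | 84% | 167 | 33% / 84% |
| 20% | 18 v 22 | 12% | 18 v 26 | 38% | 134 | 26% / 74% |
| 40% | 31 v 34 | 7% | 31 v 37 | 18% | 100 | 19% / 59% |
| 60% | 44 v 46 | 5% | 44 v 48 | 10% | 67 | 11% / 38% |

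**Combined group versus placebo (334 v 167).** For 5% v 10%, power is 47% with no ideators and 16% at b = 20%. For 5% v 15%, it is 94% and 51%.

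**Other emergent rates, no baseline ideators, pairwise.** A doubling has 10%, 18%, 56% and 69% power at 2%, 3%, 8% and 10%. A tripling has 35%, 56%, 98% and over 99%. With b = 20% and half positive again, the tripling figures are 11%, 19%, 77% and 90%.

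**Offsetting, illustrated.** Take b = 40%, persistence 70% on placebo and 60% on active, emergent risk 5% and 10%.

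- Placebo: 0.28 + 0.03 = 31%
- Active: 0.24 + 0.06 = 30%

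Emergent risk has doubled, yet the tested rate is lower on active.

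**What an interval would show.** Suppose emergent counts are 7/134 in both arms. Fisher gives p = 1.0. The log-scale standard error of the risk ratio is √(2 × (1/7 − 1/134)) = 0.52, so the 95% CI is exp(±1.96 × 0.52) = 0.36 to 2.8. The Newcombe interval for the risk difference is −5.8 to 5.8 points. Equal counts do not exclude a doubling. With 13/134 versus 7/134, p = 0.25 and the Newcombe interval is −2.0 to 11.2 points.

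**The case against.** The trial was sized on MADRS, and limited power for uncommon safety events follows from that. The protocol planned description only, so the Fisher test already goes beyond it. Neither document says that a non-significant result will be read as absence of risk. Exclusions 2 and 4 narrow the pool of ideators beyond exclusion 3, so the higher assumed prevalences may not occur. The output templates that accompany the SAP are not visible and might contain intervals. All of this is fair, but the SAP text specifies an inferential comparison for suicidality and should specify a usable one. It already does so for mania.

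A reader might infer three stronger things that do not hold.

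- **That the test would usually miss a tripling as well as a doubling.** That depends on rates the documents do not give. Power for 5% versus 15% is 84% with no baseline ideators, and 51% for the combined group even at 20% ideators with 70% persistence.
- **That the p-value is the only between-arm evidence.** Emergence, worsening, attempts and completed suicides are tabulated by arm, as are adverse events. Appendix 1 requires percentage denominators to be identifiable, so a reader could form an interval by hand. The signal is displayed; it is only the inference that is missing.
- **That counting baseline ideators is the whole cause of low power.** Testing emergence alone still has only 11 to 26% power for 5% versus 10% at 20 to 60% ideators. Few events at this sample size is the other cause.

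**Conclusion.** The concern holds in a limited form. The only formal between-arm suicidality comparison is a Fisher test on a composite that takes no account of baseline status, with no effect estimate or interval specified. On assumed rates, the overall pairwise test would usually miss a doubling at emergent rates up to about 5% (power 33% at best for 5% versus 10%). It would usually miss a tripling only where the emergent rate is low (35% power at 2% versus 6% with no ideators) or baseline ideation is common (38% or less for 5% versus 15% from 20% ideators upward at 70% persistence).

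Moving to emergence improves power for a tripling but not enough for a doubling. The main gap is therefore the missing interval, more than the choice of tested variable. The absence of an estimate and the disregard of baseline status can be read directly from SAP 16.7.4 and need no assumption; the size of the effect on power rests entirely on assumed prevalence, persistence and emergent risk.

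**What to change.** In SAP 16.7.4, add for each dose and for the combined group versus placebo the risk difference with an exact or Miettinen-Nurminen 95% CI for:

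- emergence of suicidality, with patients free of suicidality at baseline as the stated denominator;
- worsening of ideation, among all patients with baseline and post-baseline data.

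State that any conclusion that suicidality is not increased rests on the upper confidence limit and not on a non-significant p-value. The Fisher test on any suicidality may stay as a supplementary summary.

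The cost is a paragraph of SAP text and an added column in tables already planned, with no new data. The downside is that the intervals will be wide and the reassurance they offer weaker than a bare p-value might suggest.
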